Adapted ACHIEVE Curriculum for Community Mental Health Settings

NCT03999892

Protocol approval date 6/13/2019

[name], MHS

JHM IRB - eForm A – Protocol

1. Abstract

Prevalence of obesity is significantly elevated and a leading cause of preventable death in people with serious mental illness (SMI) through its effects on other cardiovascular disease (CVD) risk factors and CVD. Behavioral interventions targeting changes in diet and exercise need to be tailored to the needs of people with SMI, such as memory impairment and limited executive function. The NIMH-funded Achieving Healthy Lifestyles in Psychiatric Rehabilitation (ACHIEVE) trial tested a behavioral weight-loss intervention for persons with SMI and demonstrated clinically significant weight loss. In light of the obesity epidemic in persons with SMI, there is an urgent need to scale-up interventions like ACHIEVE. To increase ease of adoption and sustained implementation of ACHIEVE in community mental health programs, the format needs to be adapted for delivery by community mental health staff. Based on our experience conducting the ACHIEVE trial, this study team has already made modifications to adapt the ACHIEVE intervention into ACHIEVE-Dissemination or “ACHIEVE-D” curriculum for community mental health settings. Therefore, we will pilot test two months of this ACHIEVE-D curriculum in a community-based psychiatric rehabilitation program (PRP) to determine whether this format is acceptable to participating PRP consumers with SMI as well as PRP staff and peer leaders.

This pilot study protocol is the first part of an NIMH R34 study that will test strategies to increase implementation of ACHIEVE. The second part of the R34 study, which will test the complete version of ACHIEVE-D in multiple study sites, will be submitted as a change in research or a separate protocol. This R34 is part of a P50, the NIMH Johns Hopkins ALACRITY Center.

2. Objective

To pilot test two months of the adapted ACHIEVE-D curriculum at a single PRP.

Hypothesis 1: The adapted ACHIEVE-D curriculum will be acceptable to individuals with SMI.

Hypothesis 2: The adapted ACHIEVE-D curriculum will be feasible and acceptable to PRP staff and peer leaders in promoting weight loss and lifestyle behavior change among consumers with SMI at their center.

3. Background

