In this study, we will pilot test two months of the ACHIEVE-D curriculum in a community-based psychiatric rehabilitation program (PRP) to determine whether this format is acceptable to participating PRP consumers. The study team has prior experience collecting qualitative and quantitative data and delivering interventions among persons with SMI and has a long-term relationship with the study site (Prologue, Inc.) where this research will be conducted.

4. Study Procedures

a. Study design

We will conduct a pre/post study of two months (8 weeks) of the ACHIEVE-D curriculum. We will conduct a focus group among mental health consumers, as well as secondarily compare their outcomes pre- and post- intervention. The study will invite PRP staff as well as peer leaders to observe all the sessions during this pilot. We will conduct a focus group among PRP staff and peer leaders who observe the intervention sessions. Our primary outcomes will be to determine the acceptability and feasibility of the adapted curriculum.

Description of ACHIEVE-D Intervention

We will test two modules of the adapted video-assisted curriculum format (Tables 1 & 2).

Consumers will participate in 45 to 60-minute multipurpose classes three times per week, which will include a segment on group weight management (~20-30 minutes) and group exercise (~20-30 minutes). Within each module, the group weight management topic varies by week, and within each week the content of the three weight management groups builds gradually and is purposely repeated. Within each module, the group exercise classes will focus on mild to moderate intensity aerobic exercise using an exercise video. The class will have a progression of

intensity and duration appropriate for sedentary individuals. Classes will start at a lower intensity for 10-15 minutes and gradually progress to moderate intensity aerobic exercise for 20-30 minutes per session across the two-month period. Participants will also be encouraged to engage in moderate intensity exercise, such as brisk walking, of similar duration on days when they are not at the PRP. In this pilot study, a trained study interventionist will deliver the ACHIEVE-D curriculum, as our aim is to determine acceptability of this new format with consumers, PRP staff and peer leaders prior to training the PRP staff and peer leaders to deliver the content, which is planned for a subsequent study.

Procedures related to Hypothesis 1 – Consumers with SMI

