Recruitment. We will recruit participants from Prologue, which is a PRP based in Baltimore with whom the study team has a long-term relationship (see letter of support). We will use similar methods as in prior and ongoing studies. We will recruit consumers with SMI who are willing to participate and have no contraindications to participating in a diet and physical activity program (see eligibility criteria described in following section).

We will make presentations during regular consumer meetings at the PRP where we will provide information about the study. We will also display recruitment flyers in the PRP (Flyer). We will use a telephone script to handle all calls or in-person inquiries generated from these presentations and flyers (Screening Script). Consumers who are interested in participating will sign up to attend a consent/screening visit. To address privacy issues during recruitment, all participants who are contacted or who approach us for recruitment will be assured that the research staff at Johns Hopkins will be the only ones to see their information, and that the information we collected will be kept private and be used only for the research study we are discussing. If the potential participant chooses not to enroll in the study or does not qualify to be in the study, then his/her information will be destroyed.

Consent & Screening. We plan to screen a total of 20 consumers with the goal of enrolling approximately 10 into the study. Participant eligibility will be determined at the consent/screening interview (Table 3).

Consent

The study will be explained in detail to the potential participants in a one-on-one format onsite at the PRP in a private room. Informed consent for the study will be obtained from each eligible participant at the beginning of this visit (Consumer Written Consent). In particular, consumers will be advised of the voluntary and confidential nature of participation. Consumers will be asked questions about the study procedures to test their understanding. They will also be provided the contact information of the principal investigator. We will emphasize that their participation in the study will not affect their care at the PRP or Johns Hopkins. After consent is obtained, then potential participants will be screened.

Screening

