At the end of the pilot period, we will conduct a 90-minute focus group with PRP staff and peer leaders who were able to observe at least two sessions of the ACHIEVE-D curriculum to explore their perceived feasibility of delivering such a program as well as their satisfaction with program content and format. Informed consent will be obtained from each participant on the day of the focus group (Staff & Peer Leader Oral Consent). We will use a private room in the PRP for this group. We use a moderator guide for the focus group (Staff & Peer Leader Focus Group Moderator Guide), and will show them video recorded of the pilot intervention session(s) to facilitate the discussion and prompt feedback. The focus group will be tape-recorded and conducted by a moderator. The focus groups will be transcribed by Production Transcripts. Names will be removed from transcripts and replaced with ID numbers. After transcription, recordings will be destroyed.

- b. Study duration and number of study visits required of research participants.
We anticipate that the total duration for all study procedures to be 4 months, and the intervention will take 2 months. Consumers will participate in a focus group as well as complete baseline and post-intervention data collection visits. PRP staff and peer leaders will participate in a focus group. Study visits and focus groups will be held onsite at the PRP.
- c. Blinding
Not applicable
- d. Justification of why participants will not receive routine care or will have current therapy stopped.
Not applicable
- e. Justification for inclusion of a placebo or non-treatment group.
Not applicable
- f. Definition of treatment failure or participant removal criteria.
Not applicable
- g. Description of what happens to participants receiving therapy when study ends or if a participant's participation in the study ends prematurely.
Not applicable

5. Inclusion/Exclusion Criteria

For consumers with SMI to participate in the pilot, they must be aged 18 and older and are consumers at Prologue psychiatric rehabilitation program. In addition, we will require that these consumers are 1) Expected to be in the rehabilitation program for at least 6 months after enrollment in intervention and able to attend the intervention classes 3 days per week, 2) Able and willing to give informed consent and participate in the intervention, 3) have a BMI over 25 kg/m² (overweight or greater), and 4) be interested in losing weight.

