The 2018 Physical Activity Readiness Questionnaire (2018 PAR-Q+) will be administered to triage participants within the ACSM Exercise Pre-Participation Health Screening Logic Model. For persons who require medical clearance according to these ACSM guidelines, we will refer them to their physician and send a letter to this physician informing them that the patient is planning on enrolling in the study (Physician Approval for Exercise Letter). We will ask for a fax-back form with medical clearance from the physician for the individual to participate. The ACSM guidelines define medical clearance as approval from a health care professional to engage in exercise, on the basis of the presence of signs or symptoms and/or known cardiovascular, metabolic, or renal disease and physical activity status. The term "medical clearance" has replaced specific recommendations for a medical examination or exercise test because it should be the health care provider who decides what evaluation, if any, is appropriate before the initiation of a moderate-intensity exercise program as proposed in ACHIEVE-D.

For PRP staff or peer leaders to participate, they must be at least 18 years old and have observed at least two ACHIEVE-D sessions.

6. Drugs/ Substances/ Devices

Not applicable

7. Study Statistics

a. Primary outcome variables.

All focus groups will be audio recorded and transcribed verbatim. Research assistants will check the transcripts for accuracy. Two investigators will identify meaningful segments within the responses and assign codes using an editing style analysis technique for each focus group transcript. We will group codes into themes and discuss these themes among the entire team of investigators. We will use Atlas.ti 5.2 software to facilitate qualitative data management and analysis. The study team will also review the transcripts and make modifications to the intervention materials and study procedures for a future trial based on these results.

b. Secondary outcome variables.

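### Does destroying the records of consumers who decline or do not qualify leave the pilot unable to say what it needs to about uptake and the 3-day attendance condition?

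*Combined protocol and SAP*

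**What the plan says.** The destruction sentence closes the Recruitment text in Section 4, in the part that deals with privacy: if a potential participant "chooses not to enroll in the study or does not qualify to be in the study, then his/her information will be destroyed". It states no exception for counts or reasons.

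Under Consent & Screening the target is: "We plan to screen a total of 20 consumers with the goal of enrolling approximately 10 into the study". Eligibility is settled at that visit, after consent has been obtained. Section 5 requires consumers to be "able to attend the intervention classes 3 days per week", in the same numbered criterion as "Expected to be in the rehabilitation program for at least 6 months after enrollment in intervention".

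On purpose, the end of Section 3 says the pilot is meant "to determine whether this format is acceptable to participating PRP consumers". Section 4a makes acceptability and feasibility of the adapted curriculum the primary outcomes, and Table 3 lists the two focus groups under that heading. Section 7a says the team will review the transcripts and "make modifications to the intervention materials and study procedures for a future trial based on these results". The Abstract describes what comes next: "The second part of the R34 study, which will test the complete version of ACHIEVE-D in multiple study sites".

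**The concern.** A feasibility pilot is often expected to report participant flow: how many were approached or inquired, how many were screened, how many enrolled, and why the rest did not. Here the records of those who drop out before enrolment are destroyed, and no log is described. The Consent/Screening column of Table 3 has no item for disposition or reason. The participation measures in Section 4 start only after enrolment, and Section 7 has no participant-flow summary.

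The 3-day condition sharpens the worry. Attendance is read as a sign of acceptability, yet it is observed only in people already judged able to come three days a week. If many consumers were excluded on that ground, the multi-site study would want to know. The consumer focus group cannot say, because it hears only from people who took part, and destroyed reasons could not be reconstructed.

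**Working it through.** No sample-size or power figure is at issue, since Section 7c gives none. The check is what can still be counted, what cannot, and whether any planned result depends on the missing part.

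**Inputs**
- Planned screened: 20; planned enrolled: about 10 (Section 4, Consent & Screening).
- Classes: 3 a week for 8 weeks, 24 in all (Section 4, session video recording).
- Attendance mark: 80% of sessions (Section 4, Acceptability).
- Number of inquirers: not given.
- Number failing the 3-day condition: not given.

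**What can still be counted**
- Planned non-enrolled among screened: 20 − 10 = 10, and 10/20 = 50%.
- Planned yield: 10/20 = 50%. This is a target and not an observation, so a confidence interval around it would mean nothing.
- The actual screened and enrolled totals do not need the destroyed records. Screening is a scheduled, consented visit with a $10 payment (Section 10), and ID numbers are assigned at recruitment (Section 8b).

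**What is not secured by the text**
- Uptake among inquirers. With 10 enrolled and an assumed 20, 30, 40 or 60 inquirers, uptake would be 10/20 = 50%, 10/30 = 33%, 10/40 = 25% or 10/60 = 17%. These denominators are assumptions that show the range only.
- Losses to the 3-day condition among those screened: from 0/20 = 0% to 10/20 = 50%. This range says only that somewhere between none and all of the non-enrolled fell to that condition.

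**How much a tally would add**
- Suppose a tally showed that none of 20 was lost to the condition. The exact two-sided 95% upper limit is 1 − 0.025^(1/20) = 0.168, or 17%. Even that clearest result, from one site, would be descriptive.

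**Does any planned result depend on it?**
- Focus-group themes come from enrolled consumers and from observing staff and peer leaders. Reasons for non-enrolment are not an input.
- The satisfaction questionnaire, class attendance and the pre/post diet and activity comparisons all concern enrolled consumers.
- Hypothesis 1 concerns acceptability to consumers. Hypothesis 2 places feasibility with staff and peer leaders, who have their own focus group. Recruitment yield is in neither.

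**Does the 3-day condition clash with the class schedule?** The Class Timing paragraph in Section 3 says that three classes a week with repeated content help a consumer who misses one. Section 5 asks that consumers be able to come three days a week. A person who is able to come three times can still miss a class now and then, so the two statements agree. Table 1 also shows that the parent ACHIEVE trial held exercise classes three times a week, so the frequency is not new.

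**The case for a change.** The strongest case for a change is that the loss is irreversible, the remedy is cheap, and the pilot exists to inform a larger study. The 80% attendance mark adds weight. Of 24 sessions, 80% is 19.2, so at least 20 must be attended. Someone who can come only two days a week could reach 2 × 8 = 16 of 24, or 67%. The entry condition therefore removes people who could not have met the mark, and no described record shows how many.

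The arithmetic stands, and so does the limit on generalising: attendance in this pilot describes consumers who could commit to the schedule. A reader can see that from the eligibility criteria, and the aim is stated for participating consumers. A tally would show how many were set aside; it would not change the attendance result or make it wrong.

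Nor is it established that the information will be lost. The sentence concerns an individual's information, and a count without names is not plainly within it. The Screening Script that handles inquiries is not among the documents available for review and may already have a reason field.

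A tally also has small costs. It would cover people who never consented, at a single named programme, who are told their information serves only the study being discussed. Without identifiers, repeat inquirers could not be separated, which would blur the inquiry denominator the tally is meant to supply.

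**Conclusion.** No change to the plan is needed. The protocol is silent on whether anonymous counts and reasons for non-enrolment are kept before individual records are destroyed. That is missing reporting detail, which a study team can fill sensibly when it writes up participant flow. About 10 of the 20 planned screened consumers would have records destroyed, and the share lost to the 3-day condition is unknown within 0% to 50%. No hypothesis, outcome or test uses that share, and the screened and enrolled totals remain available.

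This rests on two readings: that the destruction sentence covers identifiable records and not bare counts, and that the aim is limited, as stated, to consumers who take part. If the team wishes, it can keep an anonymous tally of stage reached, outcome and broad reason, match the privacy assurance to it, and report it descriptively beside attendance. That would help the designers of the multi-site study a little, but the soundness of this pilot does not depend on it.

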(2) **Class Timing:** ACHIEVE-D multi-purpose classes will be held three times a week; this schedule will make it easier for consumers to receive the curriculum if they miss one of the groups, eliminating the need for make-up sessions. Within each monthly module (Table 2), topic varies by week. In the three group weight management + exercise classes each week, content builds gradually but is largely repeated; repetition of messages is a key tenet of intervention tailoring for SMI. This format will also provide frequent opportunities for on-site exercise.

Table 2. ACHIEVE-D Monthly Modules (and Example Weekly Topics)

Weight Loss Success (e.g., What Does it Mean to Watch What You Eat?)
Avoiding Sugar Drinks (e.g., Drinking Enough Water)
Avoiding Junk Food (e.g., Avoiding Junk Food by Making Smart Choices)
Eat more Fruits and Vegetables (e.g., Adding Fruits & Veg to Your Meals)
Eat Smart Portions (e.g., Slowing Down for Smart Portions)
Smart Snacking (e.g., Creating Smart Snack Habits)

(3) Video-Assisted Content: In the ACHIEVE trial, mental health program staff used videos to successfully deliver exercise classes; we will use the same exercise video approach in ACHIEVE-D. In addition, we have developed weight-loss content videos for each week of the curriculum. Each 5 to 10-minute video segment will assist coaches and peer leaders in delivering the evidenced-based weight management content (e.g., video showing consumers reviewing the calorie and sugar content in various beverages). In class, the coach will introduce the weight management topic using the video, followed by discussion. Coaches will stop and start videos as-needed, emphasize repetition of content, and use motivational interviewing techniques to evoke consumers' confidence and competence to implement each ACHIEVE-D behavior.

(4) Peer Leaders: In ACHIEVE-D, peer leaders will support ACHIEVE-D coaches in curriculum delivery. Specifically, peers will role-model behaviors for the entire group, particularly during the group exercise sessions; help participants with SMI set realistic individualized behavioral goals; and encourage consumers' with SMI to consistently attend class. Because of their common SMI experience, peers are in a unique position to demonstrate empathy and support consumers in behavior change.

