Procedures. This data will be collected during study visits at baseline and follow-up for enrolled participants held onsite at the PRP in a private room. Surveys will be administered in-person by trained research assistants. All data will be collected on Johns Hopkins encrypted, password protected laptop computers and entered into a RedCap database. Because of consumers' generally low literacy and problems with cognition, all instruments will be interviewer administered to decrease the burden on participants and improve validity of data collection. Enrolled participants will complete baseline data collection measures (Table 3).

During the intervention, we will also collect data on participants regarding attendance, weight from weigh-ins during the sessions, hours per week each consumer participated in ACHIEVE-D exercise classes, as well as diet and physical activity via weekly self-reported logs.

We will video record each class session (3 classes per week for 8 weeks – 24 sessions total) and grade the sessions using a fidelity tool (ACHIEVE-D Fidelity Tool), which measures to what extent the coach implements the core components of ACHIEVE-D and uses a motivational interviewing delivery style. Once videos are evaluated for fidelity, any that are not needed will be destroyed; some will be stored on a Johns Hopkins secure network drive and used for future training in fidelity monitoring. In addition, short video clips from these sessions may be incorporated into materials for the larger R34 study including to train coaches.

After completion of the intervention, consumers will complete a survey including asking questions regarding satisfaction with the curriculum, self-reported sugar sweetened beverages and sedentary behaviors, and anthropometric measurements will be repeated at this time. We will also repeat other measures as described in Table 3.

Table 3. Data Collection Schedule

	Consent/ Screening	Baseline	Follow-up	
			During	Post
Informed consent	x			
Demographics	x			
Medical history	x			x
Medications	x			
Substance use (ASI-Lite)	x			
Exercise pre-participation screening (2018 PAR-Q+)	x			
Weight	x	x	x	x
Height	x			x
Primary Outcomes				
Consumer focus group				x
PRP staff & peer leader focus group				x
Secondary Outcomes				
Diet				
EARLY Eating Away from Home Q		x		x
EARLY SSB Consumption Q		x		x
Physical Activity				
CARDIA/EARLY Q – sedentary behavior		x		x
Eating Behaviors				
Palatable Eating Motives Scale (PEMS) – Coping Subscale		x		x

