Trait Food Craving Q – Reduced Form		x		x
Reward-based Eating Drive (RED) Scale		x		x
Psychological & Support				
Perceived Stress Scale (PSS)		x		x
Important Others' Q		x		x
Anthropometric Measurements				
Waist circumference		x		x
Process Measures				
Consumer attendance & exercise at group sessions			x	
Consumer food and physical activity logs			x	
Consumer Satisfaction Q - Nabati				x
Coach Fidelity to ACHIEVE-D			x	

Abbreviations: SSB – sugar-sweetened beverage; Q – questionnaire

Below we describe the planned secondary outcomes:

Acceptability

A 12-item Consumer Satisfaction Questionnaire based on the instrument developed by Nabati and colleagues will be used to determine acceptability. Following the intervention, in addition to the focus group, we will use this standard measure of satisfaction with the intervention. We will also examine participation as a reflection of acceptability. Participation in intervention sessions will be measured by attendance at the group classes, the number of sessions attended, and proportion attending at least 80% of sessions.

Date: May 15, 2019

Principal Investigator: [name]

Application Number: IRB00194122

Diet

We will administer the EARLY Sugar-Sweetened Beverage (SSB) questionnaire at baseline and post-intervention, which has been selected by the NIH as Accumulating Data to Optimally Predict Obesity Treatment (ADOPT) Core Measures for diet.

Physical Activity

We will administer the sedentary behavior inventory from CARDIA/EARLY at baseline and post-intervention, which has been selected by the NIH as ADOPT Core Measures for self-reported physical activity.

Weight & Waist Circumference

Weight will be measured at baseline and post-intervention using standard procedures as described in the screening section above. Waist circumference is measured using a tape, according to a standardized protocol at baseline and post-intervention.

Below we describe the other planned survey measures in this study:

Demographics

Most demographic data will be obtained from Prologue's intake assessment, but we will obtain updated marital status and living arrangements as well as confirm educational level. This data will be collected at the screening visit.

Medical History

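### Does the 80%-of-sessions measure wrongly count against consumers who miss classes that the format allows them to miss?

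*Combined protocol and SAP*

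**What the plan says.** The Acceptability paragraph of Section 4 uses a 12-item satisfaction questionnaire and also looks at participation as an indicator of acceptability. Participation is summarised in three ways: attendance at the group classes, the number of sessions attended, and the "proportion attending at least 80% of sessions". The number of sessions is given under the secondary outcome procedures of Section 4: "3 classes per week for 8 weeks – 24 sessions total".

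Section 3, item (2) Class Timing, explains the schedule. It makes it "easier for consumers to receive the curriculum if they miss one of the groups, eliminating the need for make-up sessions". The same item says "Within each monthly module (Table 2), topic varies by week", and that across the three classes of a week "content builds gradually but is largely repeated". The description of the intervention in Section 4a repeats this for the pilot: "within each week the content of the three weight management groups builds gradually and is purposely repeated". Each class also has an exercise segment of about 20 to 30 minutes, which starts at a lower level and is to "gradually progress to moderate intensity aerobic exercise for 20-30 minutes per session across the two-month period".

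**The concern.** Read together, these statements seem to conflict. If the distinct unit of content is the week, and three classes a week are offered so that one can be missed, then a measure that weights all 24 classes equally and draws a line at 80% appears to penalise the very behaviour the format was built to absorb. The plan gives no reason for choosing 80%.

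If the point held, a low proportion above the line could be read as poor acceptability of a format that had in fact worked as intended, and that reading could be carried into the later multi-site study. The pilot exists to judge acceptability of the format before programme staff and peer leaders are trained to deliver it, so a misleading acceptability measure would matter.

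**Working it through.** **Inputs.** From the documents: 3 classes a week for 8 weeks; threshold 80%; about 10 consumers to be enrolled (Section 4, Consent & Screening). Not in the documents: the chance *p* that a consumer attends a given class. I assume it is constant and independent across classes and vary it.

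**1. The threshold in sessions.** 3 × 8 = 24, which reproduces the plan's total. 0.80 × 24 = 19.2, so 20 sessions are needed and 4 may be missed.

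**2. Attendance patterns.**

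| Pattern | Sessions | Share | Reaches 80%? |
|---|---|---|---|
| One class missed in 4 of 8 weeks | 20 | 83.3% | yes |
| One class missed in 5 of 8 weeks | 19 | 79.2% | no |
| One class missed in all 8 weeks | 16 | 66.7% | no |
| One whole week plus one other class missed | 20 | 83.3% | yes |
| One class attended in each week | 8 | 33.3% | no |

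The line does not track weekly topic coverage in either direction.

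**3. How often the pattern in question occurs.** The pattern is at least two classes in every week but fewer than 20 in total, which means exactly one miss in 5 or more weeks:

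Σ (k = 5 to 8) C(8,k) · [3p²(1−p)]^k · [p³]^(8−k)

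| p | P(20 or more of 24) | P(at least 1 class every week) | P(at least 2 every week, under 20 in total) |
|---|---|---|---|
| 0.60 | 0.013 | 0.589 | 0.023 |
| 0.70 | 0.111 | 0.803 | 0.072 |
| 0.75 | 0.247 | 0.882 | 0.093 |
| 0.80 | 0.460 | 0.938 | 0.092 |
| 0.90 | 0.915 | 0.992 | 0.022 |

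At its highest tabulated value this is 10 × 0.093 = 0.9 of a person among 10.

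**4. Does a consumer below the line have the whole curriculum?** The documents do not say so. Content builds within the week and is only largely repeated, so the three classes are not interchangeable. Item (2) of Section 3 treats repetition as central to tailoring for SMI, so it is part of the intervention rather than spare capacity. It also names frequent on-site exercise as a further benefit of the schedule. A repeat of the topic does not replace a missed exercise segment.

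**5. What the plan does with the proportion.** Section 7b names programme attendance as an acceptability outcome, without a threshold. Section 4f marks treatment failure as not applicable. Section 7a bases changes to materials and procedures for the future trial on the focus-group transcripts. No passage sets a target for the 80% proportion or ties a decision to it.

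**6. Would a weekly measure be better?** Consider the share of consumers with at least one class in 7 or more of the 8 weeks. It can be met with 7/24 = 29% attendance. At p = 0.50 the weekly chance is 1 − 0.5³ = 0.875, and 0.875⁸ + 8 × 0.125 × 0.875⁷ = 0.344 + 0.393 ≈ 0.74, so about 74% would qualify while skipping half the classes. At p = 0.667, 0.75 and 0.80 the same formula gives 0.967, 0.994 and 0.998, where it separates almost nobody. It is not spared the small sample either: 3/10 has a 95% Clopper-Pearson interval of 7% to 65%, and 10/10 has one of 69% to 100%.

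**The case for a change.** The strongest case for the concern counts a topic as met after a single class. On that reading the gap is large. Under the same independence model, about 64% of consumers at p = 0.75 and about 48% at p = 0.80 would attend at least one class on every topic and still fall short of 20 sessions. A reader who saw only that 25% reached 80% might conclude that the format was disliked. A total of 16 sessions also cannot show whether someone came twice every week or missed several weeks outright. Weeks attended could be tabulated from the attendance record at no cost.

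The arithmetic stands, and so does the remark that 80% is unexplained. The inference does not. One class of three is not the week's content when content builds, and it is a third of the week's exercise segments. Independence also favours the argument: if absences cluster into whole weeks, topic coverage falls. The reader will not see the proportion alone, because the number of sessions attended and the satisfaction questionnaire are reported too, and hours per week in the exercise classes are collected. Eligibility requires that consumers be able to attend three days a week (Section 5), so someone who can come to three classes and regularly comes to two is telling the investigators something about acceptability. Adding weeks attended would be a reasonable extra line in a table, but its absence distorts no planned result.

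**Conclusion.** The concern does not hold. The 80% line does mean 20 of 24 sessions, and missing one class every week does give 67%. But the measure describes willingness to attend, for which all classes offered are a coherent denominator. It does not claim to measure receipt of content, and it classes nobody as a failure. It is one descriptive secondary summary among several, in a pilot of about 10 consumers whose primary outcome is qualitative.

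The pattern at issue, at least two classes every week yet fewer than 20 in total, would affect about 2% to 9% of consumers. That range assumes constant, independent attendance of 60% to 90% per class, an assumption the documents neither give nor contradict. The conclusion does not rest on it: it rests on the purpose stated for the measure and on the absence of any rule attached to it. It would change if a later version of the plan made the 80% proportion a criterion for proceeding.
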